#### 1.1.1. Gastric Adenocarcinoma

Adenocarcinoma of the stomach is the most common gastrointestinal cancer in the world and the third leading cause of cancer death worldwide {[Ferlay 2013](#)}. Approximately 22,220 patients are diagnosed annually in the United States, of whom 10,990 are expected to die. While the incidence of distal gastric adenocarcinoma has recently declined in the United States, gastric cancer remains quite frequent in certain minority populations and it is still the second most

common cause of cancer death worldwide. In addition, adenocarcinoma of the gastroesophageal junction (GEJ) is one of the most rapidly increasing solid tumors in the United States and Western Europe.

Most patients with gastric cancer in the United States are symptomatic and already have advanced incurable disease at the time of presentation. At diagnosis, approximately 50 percent have disease that extends beyond locoregional confines, and only one-half of those who appear to have locoregional tumor involvement can undergo a potentially curative resection. Surgically curable early gastric cancers are usually asymptomatic and only infrequently detected outside the realm of a screening program. Screening is not widely performed, except in countries which have a very high incidence, such as Japan, Venezuela, and Chile. The common presenting symptoms and diagnostic approaches to gastric cancer include weight loss (usually results from insufficient caloric intake rather than increased catabolism) and may be attributable to anorexia, nausea, abdominal pain, early satiety, and/or dysphagia. Abdominal pain is often present which tends to be epigastric, vague and mild early in the disease but more severe and constant as the disease progresses. Dysphagia is a common presenting symptom in patients with cancers arising in the proximal stomach or at the esophagogastric junction. Patients may also present with nausea or early satiety from the tumor mass or in cases of an aggressive form of diffuse-type gastric cancer called linitis plastica, from poor distensibility of the stomach. They may also present with a gastric outlet obstruction from an advanced distal tumor.

In metastatic disease, multiple single agent studies using drugs such as cisplatin, docetaxel, 5-fluorouracil (5-FU), and irinotecan among others have demonstrated modest activity. Treatment of metastatic HER2 negative cancer in the first line setting consists of combination chemotherapy with a triplet or doublet regimen. The triplet regimen of docetaxel/cisplatin/5-FU is the only approved combination in the United States. Because of significant toxicity, this combination is reserved for patients who are medically fit and have good performance status. The National Comprehensive Cancer Network guidelines for the treatment of metastatic disease recommend a 2-drug regimen. A common regimen includes a fluoropyrimidine (5-FU or capecitabine) and platinum agent (cisplatin or oxaliplatin). The current standard of care for patients who progress on front line regimens remains controversial. While many patients are treated in the second line setting with taxanes, some are treated with irinotecan either by itself or in combination with a taxane. Ramucirumab, an anti-vascular endothelial growth factor receptor 2 antibody, was recently approved in the United States as monotherapy or in combination with paclitaxel to treat gastric and GEJ cancer that has progressed after treatment with a fluoropyrimidine- or platinum-containing regimen. While there is no clear standard regimen for this disease, there is also a lack of clinical trials addressing this patient population. The majority of patients with adenocarcinomas of the esophagus and stomach are diagnosed with either stage III or IV disease and the prognosis is very poor with 5-year survival rates between 5-15%. Treatment options after first-line therapy are still limited in the metastatic setting. Traditional cytotoxic chemotherapy regimens for second and third-line treatment in patients with metastatic disease have shown a median overall survival ranging from 3-5 months compared to 2.4-3.6 months for best supportive care {[Ford 2014](#), [Kang 2012](#), [Thuss-Patience 2011](#)}.

### **1.1.2. MMP9 Expression in Oncology**

Matrix metalloproteinase 9 is expressed by tumor epithelia as well as infiltrating macrophages, other inflammatory cells, fibroblastic stroma, and tumor-associated endothelial cells. Expression of MMP9 by tumor epithelia in particular has been implicated in many pro-tumorigenic processes and is associated either with loss of tumor suppressor or gain of oncogenic activity, as a temporal response to oncogenic changes in local tumor environment, or during processes such as invasion and proliferation. MMP9 expression by tumor-associated macrophages, neutrophils, mesenchymal-derived suppressor cells and other cell types in in the tumor microenvironment is also associated with local pro-tumorigenic immunomodulation and angiogenesis {Farina 2014}. In gastric tumors, MMP9 expression is consistently observed, often in both tumor epithelia and stromal compartments.

## **1.2. General Information**

GS-5745 is a humanized monoclonal antibody that binds with high affinity to human MMP9, but not to other human MMPs. GS-5745 was derived from the murine anti-human MMP9 monoclonal antibody, AB0041, and shares the same binding characteristics. GS-5745 and AB0041 cross-react with and inhibit rat and cynomolgus monkey MMP9 but not murine MMP9. AB0046, which cross-reacts with and inhibits murine MMP9, was generated via immunization in MMP9 knockout mice. Epitope mapping analysis revealed that AB0046 binds a similar region in murine MMP9 to that bound by GS-5745 and AB0041 on human MMP9.

### **1.2.1. Preclinical Pharmacology and Toxicology**

#### **1.2.1.1. Pharmacology**

The therapeutic potential of inhibitory antibodies targeting human MMP9 (AB0041) and mouse MMP9 (AB0046) was evaluated in a surgical orthotopic xenograft mouse model of colorectal carcinoma in which tumors were derived from the human tumor cell line HCT116. In this treatment model, selective inhibition of MMP9 using a cocktail of anti-human MMP9 and anti-mouse MMP9 antibodies significantly reduced growth of the primary tumor and reduced the incidence of metastases in multiple independent studies. In xenografts, treatment with either an anti-tumor-MMP9 (human) or anti-stromal MMP9 (murine) antibody yielded significant tumor growth reduction highlighting important roles for tumor epithelial-derived and stromal-derived MMP9 in primary tumor outgrowth. However, targeting of stromal MMP9 was necessary for maximum efficacy with respect to incidence of metastases, highlighting the disease-associated role of other cellular sources of MMP9 in tumorigenesis.

The major dose limiting toxicity observed in clinical studies with pan-MMP inhibitors, such as marimastat, was musculoskeletal syndrome (MSS) consisting of tendonitis manifested by joint stiffness, edema, reduced mobility, and skin discoloration. A study to evaluate the potential of an anti-MMP9 antibody to induce MSS was conducted in Lewis rats. Unlike the pan-MMP inhibitor, Marimastat, AB0041 did not induce any evidence of MSS or other toxicities in this Lewis rat MSS model.

Further details on the non-clinical pharmacology are available in the GS-5745 Investigator's Brochure (IB).

#### 1.2.1.2. Toxicology

The toxicity profile of GS-5745 has been assessed in rats and monkeys administered GS-5745 intravenous once weekly for up to 4 weeks (5 doses) at up to 100 mg/kg/dose. Target organs identified in the 4-week studies were the physal bone (rat) and adrenal gland (monkey). The physal hypertrophy in rats is likely directly attributable to inhibition of MMP9 as similar findings were observed in MMP9 null mice {Vu 1998} and in children with mutations in MMP9 and MMP13 {Lausch 2009}. In both mice and children, this is a transient finding that spontaneously regresses as the bone matures. The physal hypertrophy noted in rats is not considered relevant to adult humans because the growth plates are closed and longitudinal bone growth is no longer ongoing in adults. The relationship of the adrenal gland weight increase to MMP9 inhibition is unknown. Both the physal bone and adrenal gland findings were reversible after discontinuing GS-5745 treatment. Because these findings were minimal and/or did not impact the overall health of the animals, these findings were not considered adverse. The no observed adverse effect levels in both the rat and monkey studies were 100 mg/kg/dose intravenous once weekly for 4 weeks (5 doses).

#### 1.2.2. Clinical Trials of GS-5745

In addition to the clinical development program in solid tumors, GS-5745 is being developed for the treatment of rheumatoid arthritis and cystic fibrosis. Details of the clinical studies in these diseases can be found in the IB.

Study GS US-296-0101 is a Phase 1, open-label, dose-escalation study to evaluate safety, pharmacokinetics (PK), and pharmacodynamics following multiple intravenous administrations of GS-5745 every 2 weeks in subjects with advanced solid tumors that are refractory to or intolerant of standard treatment, or for which no standard treatment is available. Multiple doses between 200 and 1800 mg are being evaluated.

#### 1.3. Rationale for This Study

The preliminary clinical efficacy data in patients with gastric and GEJ adenocarcinoma treated with GS-5745 (800 mg every 2 weeks) and mFOLFOX6 in the Phase 1 study (GS-US-296-0101) suggests that the combination is well tolerated and has the potential to provide benefit over treatment with mFOLFOX6 alone. Serum biomarkers including the collagen neo-epitopes that are likely to reflect MMP9 enzymatic activity decrease during the first cycle of treatment with these agents. The 800 mg every 2 weeks regimen of GS-5745 is expected to reach linear range of pharmacokinetics (ie, saturate target-mediated drug disposition at trough concentrations) and to achieve steady trough concentrations greater than 26 µg/mL in majority of subjects, which is 260-fold over the IC50 (0.691 nM or 0.1 µg/mL) evaluated in enzymatic inhibitory activities of GS-5745 in vitro. Together, these data support the hypothesis that GS-5745 treatment inhibits MMP9 activity and that the inhibition may lead to improved clinical outcomes. The study aims

to assess in a randomized, blinded fashion whether GS-5745 in combination with mFOLFOX6 improves therapeutic outcomes in subjects with previously untreated locally advanced or metastatic gastric and GEJ adenocarcinoma.

### **1.3.1. Information about mFOLFOX-6**

Treatment of metastatic HER2 negative esophagogastric adenocarcinoma consists of combination chemotherapy with a triplet or doublet cytotoxic regimen. The triplet regimen of docetaxel/cisplatin/5-FU is the only approved combination in the US. Because of significant toxicity, this combination is reserved for patients who are medically fit and have good performance status. The National Comprehensive Cancer Network and European Society of Medical Oncology guidelines for the treatment of metastatic disease in the first line setting recommend a 2-drug regimen. A common regimen includes a fluoropyrimidine (5-FU or capecitabine) and platinum agent (cisplatin or oxaliplatin). There are no definitive studies demonstrating the superiority of either fluoropyrimine or platinum. An mFOLFOX6 regimen is commonly used and is acceptable in the first line setting to treat advanced esophagogastric adenocarcinoma and will be evaluated in combination with GS-5745.

### **1.4. Risk/Benefit Assessment for the Study**

GS-5745 when administered at 800 mg IV every 2 weeks in combination with standard of care chemotherapy appears to be safe and well-tolerated. The 800 mg every 2 weeks regimen of GS-5745 IV is expected to achieve steady trough concentrations greater than 26 µg/mL in the majority of subjects, which is 260-fold over the IC50 (0.691 nM or 0.1 µg/mL) evaluated in enzymatic inhibitory activities of GS-5745 in vitro. There were no dose-limiting toxicities observed at monotherapy doses up to 1800 mg IV every 2 weeks. The AE profile observed in study GS-US-296-0101 is consistent with the profile typically seen in subjects with advanced cancers including pancreatic, gastric, or non-small cell lung adenocarcinoma receiving standard of care chemotherapy. Preliminary efficacy data indicates that the objective response rate is 58% (33 evaluable subjects, data on file as of 11 September 2015) compared to the historical response rate of approximately 40% in gastric cancer patients with measurable disease treated with mFOLFOX6.

For the treatment of advanced gastric cancer, a common regimen includes a fluoropyrimidine (5-FU or capecitabine) and platinum agent (cisplatin or oxaliplatin). There are no definitive studies demonstrating the superiority of either fluoropyrimine or platinum. In the EU, in line with ESMO recommendations clinical practice guidelines {[Waddell 2013](#)}, combination regimens based upon a platinum fluoropyrimidine doublet are generally used for the treatment of metastatic advanced gastric cancer.

There is no clear or demonstrably superior standard regimen for the treatment of advanced gastric cancer and few clinical trials addressing this target patient population. Furthermore, there are limited first-line therapy treatment options in the metastatic setting. In addition, prognosis is poor in patients with adenocarcinoma of the stomach diagnosed with Stage III or IV disease.

Thus, the favorable nonclinical and clinical data outweigh the risks associated with administration of GS-5745 and hence support the evaluation of GS-5745 in combination with mFOLFOX6 as a first-line treatment in patients with advanced gastric or gastroesophageal junction adenocarcinoma.

### **1.5. Compliance**

The sponsor will conduct this study in compliance with this protocol, Good Clinical Practice (GCP), and all applicable regulatory requirements.

## **2. OBJECTIVES AND ENDPOINTS**

### **2.1. Primary Objective**

- To compare the efficacy of GS-5745 versus placebo in combination with mFOLFOX6 as measured by overall survival (OS)

### **2.2. Secondary Objectives**

- To compare the efficacy of GS-5745 versus placebo in combination with mFOLFOX6 as measured by progression-free survival (PFS)
- To compare the efficacy of GS-5745 versus placebo in combination with mFOLFOX6 as measured by objective response rate (ORR) per Response Evaluation Criteria In Solid Tumors version 1.1 (RECIST v1.1)
- To compare the safety of GS-5745 versus placebo in combination with mFOLFOX6

### **2.3. Exploratory Objectives**

### **2.4. Primary Endpoint**

- Overall survival (OS) - defined as the time from date of randomization to death from any cause

### **2.5. Secondary and Exploratory Endpoints**

The following secondary endpoints will be defined and analyzed in this study:

- Progression free survival (PFS) – defined as the time from randomization to the earlier of first documentation of definitive disease progression or death from any cause

- Objective response rate (ORR) – defined as the proportion of subjects who achieve a CR or PR as assessed by RECIST v1.1
- Safety measurements including incidence of adverse events, clinical relevant changes in laboratory values and vital signs.

The following exploratory endpoints will be defined and analyzed in this study:

### **3. STUDY DESIGN**

#### **3.1. Study Design**

This is a Phase 3, randomized, double-blind, multicenter study of GS-5745 combined with mFOLFOX6 in subjects with untreated gastric and GEJ adenocarcinoma. A total of 430 eligible subjects with advanced gastric and GEJ cancer will be randomized in a 1:1 manner to mFOLFOX6 plus GS-5745 or mFOLFOX6 plus placebo. Treatment assignment will be stratified by ECOG status (0 or 1), geographic region (Latin America or other participating countries), and primary tumor site (gastric or GEJ).

Computed tomography (CT) or magnetic resonance imaging (MRI) scans will be performed every 8 weeks to evaluate response to treatment by RECIST v1.1.

Dosage and frequency will be as follows:

- mFOLFOX6 on Days 1 and 15 of each 28-day treatment cycle for a total of 6 cycles followed thereafter by leucovorin (LV) and 5-fluorouracil (5-FU) dosing on Days 1 and 15 of each 28-day treatment cycle until disease progression. The mFOLFOX6 dosing regimen will consist of *l*-LV 200 mg/m^2 or *dl*-LV 400 mg/m^2 and oxaliplatin 85 mg/m^2 followed by bolus 5-FU 400 mg/m^2 and a 46-hour infusion of 5-FU 2400 mg/m^2.
- GS-5745/placebo 800 mg every 2 weeks until disease progression

An independent data monitoring committee (DMC) will review the progress of the study and perform interim reviews of safety data. Safety review by the DMC will be performed after the equivalent of 4 treatment cycles from the time the 60th subject is randomized. Thereafter, review of safety data will be performed at regular intervals as described in the DMC charter. In addition, the DMC will meet after approximately 33.3% and approximately 66.7% of the expected number of events have occurred to review the results from the futility and efficacy interim analysis, respectively.

#### **3.2. Study Treatments**

Subjects will receive study drug (GS-5745/placebo) on Day 1 and Day 15 of each 28 day cycle of mFOLFOX6 via intravenous infusion over approximately 30 minutes. One cycle of mFOLFOX6 consists of 2 infusions. Administration of mFOLFOX6 will be immediately after administration of study drug as described above in Section 3.1.

#### **3.3. Duration of Treatment**

Each cycle will consist of 28 days and will continue in the absence of disease progression or unacceptable toxicity, consent withdrawal or subject's refusal of treatment. There will be a screening period of up to 28 days. Following completion of treatment, subjects will be followed for safety for 55 days and survival approximately every 3 months for up to 5 years.

### **3.4. Discontinuation Criteria from Study Treatment**

GS-5745/Placebo and all of the components from mFOLFOX6 will be discontinued for any of the following reasons:

- Adverse events
- Pregnancy
- Investigator decision to remove the subject from the study treatment, in consultation with Gilead Medical Monitor
- Disease progression
- Intercurrent illness that would, in the judgment of the investigator, affect assessments of clinical status to a significant degree
- Initiation of non-study specific anti-neoplastic therapy in the absence of progression
- Subject request to discontinue treatment
- Withdrawal of consent.
  - A subject may withdraw consent solely from active participation in the study but still participate in follow up for disease progression and survival
- Death
- Discontinuation of the study at the request of Gilead, a regulatory agency, or an institutional review board or independent ethics committee (IRB/IEC)
- Lost to follow up

Should this occur, the corresponding study drug completion CRF should be entered to document the reason for discontinuation. In addition, the subject should continue with the rest of the treatment regimen and the study related procedures per protocol.

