#### 5.3.1. Dose Interruption and Reduction

If an adverse event is attributed to only 1 drug (ie, GS-5745/placebo or 1 or more component of mFOLFOX6), the investigator's discretion will be used to determine if the drug(s) not attributed to the adverse event will be withheld based on the investigator's assessment of risk-benefit of withholding 1 or more drugs (please see sections 5.3.1.1 and 5.3.1.2 for additional guidance).

Careful monitoring must be ensured for subjects with a history of allergic reactions to other platinum based chemotherapy agents. In the event of anaphylactic shock symptoms, interrupt infusion immediately and initiate appropriate treatment. Resumption of oxaliplatin treatment following anaphylactic reaction is contraindicated.

Clinically significant, abnormal 12-lead safety ECGs should be repeated. Subjects who have 2 consecutive ECGs showing a new absolute QTc duration > 500 msec, or a QT/QTc > 60 msec over the corresponding baseline value must discontinue any medications that could prolong the QT interval (including oxaliplatin). Subject's concomitant medications should be reviewed to determine a potential etiology for the ECG changes. Appropriate intervention (ie cardiology evaluation, telemetry monitoring, management of electrolyte abnormalities) in response to treatment emergent QT interval prolongation should be initiated.

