5.3.1.1. GS-5745/Placebo (Study Drug)

If a subject experiences a Grade 3 or greater toxicity considered secondary to study drug (GS-5745/placebo), treatment will be postponed until the toxicity returns to Grade 0-1 (as defined by NCI CTCAE v 4.03) or returns to the subject's baseline value. If the toxicity returns to Grade 0-1 or the subject's baseline value, the subject may resume GS-5745 at the originally assigned dose level.

If the event does not resolve to Grade 0-1 or the subject's baseline within 28 days, treatment with study drug (GS-5745/placebo) must be permanently discontinued. If the subject experiences a recurrence of the Grade 3 or greater toxicity after restarting study drug, treatment with GS-5745/placebo will be discontinued. Subjects who permanently discontinue treatment with study drug (GS-5745/placebo) may continue treatment with mFOLFOX6 after consultation with the medical monitor.

Subjects who are not receiving any chemotherapy (mFOLFOX6) should not receive study drug (GS-5745/placebo) as monotherapy. Investigators should contact the Gilead Medical Monitor with any questions regarding study drug dose modification, interruption or discontinuation.

5.3.1.2. mFOLFOX6

Recommended dose reduction for the components of mFOLFOX6 is described in [Table 5-1](#) and is based on the adverse event (AE) table described in [Appendix 5](#). Sites may also follow their institutional practice for dose reductions. Leucovorin doses may be adjusted per institutional guidelines in the event of a supply shortage.

Subjects who interrupt all components of mFOLFOX6 for greater than 28 days secondary to drug toxicity(s) that do not resolve should permanently discontinue all study treatment.

Subjects who permanently discontinue all components of mFOLFOX6 should also discontinue GS-5745/placebo.

Investigators should contact the Gilead Medical Monitor with any questions regarding study drug dose modification, interruption or discontinuation.

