**Table 5-1. Dose Reduction Levelsa for mFOLFOX6**

Drug	Dose Level		
	Starting Dose	-1	-2 b
Oxaliplatin	85 mg/m 	65 mg/m 	50 mg/m 
5-FU bolus	400 mg/m 	OMIT	OMIT
5-FU continuous infusion over 46-48 hours	2400 mg/m 	1900 mg/m 	1500 mg/m 
dl-Leucovorin/l-Leucovorin c	400/200 mg/m 	100%	100%

- a If an AE is believed likely to be due to 1 drug, it is permissible to decrease dose of that drug only.
- b Further dose levels (-3, -4, etc.) will be 20% dose reductions from the previous level for oxaliplatin and 5-FU continuous infusion. In addition, the bolus dose of 5-FU will continue to be omitted, and the leucovorin dose will remain unadjusted (100%).
- c Dosing of leucovorin will remain fixed at 100% of recommended dose.

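### Protocol 3.4 stops every agent for adverse events, then says to continue the rest of the regimen; for single-agent toxicity this contradicts 5.3.1, 5.3.1.1 and the oxaliplatin-only stops in Appendix 5

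*Protocol*

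**What the plan says.** Protocol 3.4 (Discontinuation Criteria from Study Treatment) has three parts.

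- The lead sentence: "GS-5745/Placebo and all of the components from mFOLFOX6 will be discontinued for any of the following reasons".
- A list of reasons. Adverse events come first, without grade, causality or persistence. Pregnancy, progression, withdrawal of consent, death and others follow.
- A closing instruction to complete the discontinuation form for the corresponding drug. It adds that "the subject should continue with the rest of the treatment regimen and the study related procedures per protocol".

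The toxicity rules work agent by agent. Under 5.3.1, when an event is attributed to one drug, the investigator's "discretion will be used to determine if the drug(s) not attributed to the adverse event will be withheld". Under 5.3.1.1, study drug is postponed for Grade 3 or greater related toxicity and may resume on recovery. If recovery takes longer than 28 days, "treatment with study drug (GS-5745/placebo) must be permanently discontinued". The same section then says: "Subjects who permanently discontinue treatment with study drug (GS-5745/placebo) may continue treatment with mFOLFOX6 after consultation with the medical monitor". Appendix 5 contains rules that stop oxaliplatin and no other agent.

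Section 6.4, on criteria for discontinuing study treatment, consists of a reference to 3.4 and 3.6.

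**The concern.** A mandatory stopping rule should give the same answer wherever a site looks it up. Here a site that reads 3.4, or reaches it through 6.4, is told to withdraw all first-line chemotherapy for an adverse event. A site that reads 5.3.1 or Appendix 5 is told to withhold or stop the responsible agent and may carry on with the others. The synopsis plans approximately 188 centers, so different readings are possible.

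What is at stake is mainly patient care and consistency of treatment: a patient could lose effective chemotherapy for a toxicity caused by one agent. Uneven practice could also alter exposure. It could bring forward new anticancer therapy, which censors PFS under SAP 6.2.1.1. The documents give no basis for sizing these effects.

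**Working it through.** There is no figure to reproduce and no arithmetic beyond one count, so the check sets the texts side by side.

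**Step 1: 3.4 against itself.** The lead sentence joins study drug and every mFOLFOX6 component and makes the stop mandatory. The closing sentence assumes that part of the regimen is still running. For one and the same adverse event, both cannot be followed.

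**Step 2: the lead sentence against the toxicity rules, for events attributable to one agent.**

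| Situation | Detailed rule | Lead sentence of 3.4 |
|---|---|---|
| Event attributed to one drug | 5.3.1: withholding the other drugs is the investigator's decision | all agents stop |
| Grade 3 or greater study-drug toxicity that recovers | 5.3.1.1: postpone, then resume at the assigned dose | all agents stop |
| Study-drug toxicity unresolved within 28 days, or Grade 3 or greater again after restart | 5.3.1.1: study drug stops for good; mFOLFOX6 may go on after consultation with the medical monitor | all agents stop |
| Hemolytic uremic syndrome (above Grade 3, as printed) | Appendix Table 1: oxaliplatin stops | all agents stop |
| Interstitial lung disease | Appendix Table 1: oxaliplatin stops permanently | all agents stop |
| Grade 3 paresthesia persisting between cycles; Grade 4 paresthesia | Appendix Table 2: oxaliplatin stops; by footnote a the other agents go on unless adverse events prevent it | all agents stop |

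The oxaliplatin-only stops number 1 (hemolytic uremic syndrome) + 1 (interstitial lung disease) + 2 (paresthesia) = 4.

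**Step 3: where the texts agree.** Some detailed rules do end all treatment. Appendix Table 1 ends therapy for neutropenia or thrombocytopenia that has not recovered after 4 weeks. Section 5.3.1.2 ends all study treatment when every mFOLFOX6 component has been interrupted for more than 28 days for unresolved toxicity, and adds: "Subjects who permanently discontinue all components of mFOLFOX6 should also discontinue GS-5745/placebo". These cases match the lead sentence. The contradiction is therefore confined to toxicity that the detailed rules manage by withholding or stopping one agent.

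**Step 4: does anything settle it?** Section 6.4 points only to 3.4 and 3.6. No sentence in 3.4, 5.3.1 or Appendix 5 says which governs.

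**The case against.** The strongest reply is that the intention is clear from the rest of the protocol and SAP.

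- Section 3.3 continues treatment in the absence of unacceptable toxicity, and 5.3 in the absence of toxicity that warrants stopping. In that light, adverse events in 3.4 is a category of reason, as in a disposition list, and not an order to stop at the first event.
- The closing sentence of 3.4 refers to the form for the corresponding drug, which presupposes that drugs stop separately.
- Sections 6.7 and 7.3.1 time follow-up from study drug or mFOLFOX6, whichever is stopped later. Sections 3.5 and 6.5 treat stopping all treatment as a distinct condition.
- SAP 4.1 tabulates discontinuation and its reasons separately for study drug, 5-FU bolus, 5-FU infusion, oxaliplatin and leucovorin.
- The specific sections tell the investigator what to do, with the medical monitor available. Appendix Table 2 answers the Grade 4 paresthesia case directly.
- Section 5.3.1.2 calls the dose reductions recommended and lets sites follow institutional practice for them.

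Most of this stands. It shows that drug-by-drug stopping was intended and that the practical risk is limited. It does not remove the contradiction: the intention has to be inferred against explicit wording that covers every component, and the section reserved for stopping criteria sends the reader back to that wording.

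**Conclusion.** The point holds as a wording error in an operative stopping rule. Section 3.4 contradicts itself. For adverse events attributable to one agent, it also contradicts 5.3.1, 5.3.1.1 and the four oxaliplatin-only stops in Appendix 5. It should be corrected, but it does not threaten the trial's conclusions. The number of subjects affected cannot be determined from the documents.

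Three stronger readings are not supported.

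- A reader might infer that any adverse event of any grade ends treatment, so that the dose-level entries of Appendix Table 1 and footnote a of Table 5-1 ("If an AE is believed likely to be due to 1 drug, it is permissible to decrease dose of that drug only") conflict with 3.4 as well. Those provisions set dose levels, whereas 3.4 concerns discontinuation, and 3.3 makes unacceptable toxicity the threshold.
- A reader might infer that only the adverse-event entry in the list needs attention. Investigator decision and subject request may also concern one agent or all of them, so a tally of faulty entries would mislead.
- A reader might infer that the primary analysis is compromised. OS is analysed in all randomized subjects as assigned, whichever agents they stop, and neither alpha nor the event target depends on 3.4.

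The assessment assumes that the lead sentence means what it says and that no document outside the protocol and SAP gives the detailed rules precedence.

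**What to change.** Amend 3.4 and 6.4 as follows.

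1. Change the subject of the lead sentence of 3.4 to *GS-5745/placebo and/or any component of mFOLFOX6*.
2. Replace the unqualified entry with unacceptable toxicity, and state that 5.3.1, 5.3.1.1, 5.3.1.2 and Appendix 5 determine which agents stop. This keeps their mandatory stops in force.
3. State that reasons such as progression, pregnancy, withdrawal of consent, new anti-neoplastic therapy and study termination end all treatment.
4. Limit the closing instruction to single-agent stops, subject to the existing rule in 5.3.1.1 that subjects receiving no chemotherapy "should not receive study drug (GS-5745/placebo) as monotherapy".
5. Add 5.3.1 and Appendix 5 to the cross-reference in 6.4.

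The cost is a wording amendment. Under 9.2.1 it must be submitted to the IRB/IEC and approved before it is implemented. The SAP, the sample size and data collection do not change.
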